 Other UC Campus Other institution Other community-based site Foreign Country Sovereign Native American nation (e.g. Navajo Nation, Oglala Sioux Tribe, Havasupai, etc.) 6.14 * RELYING ON AN EXTERNAL IRB: (REQUIRED) Does this application include a request to rely external IRB (a central IRB (other than the NCI CIRB) or an external IRB (other UC campus, commercial, or institutional): ○ Yes No 7.0 Research Plan and Procedures 	on an
 Other UC Campus Other institution Other community-based site Foreign Country Sovereign Native American nation (e.g. Navajo Nation, Oglala Sioux Tribe, Havasupai, etc.) 6.14 * RELYING ON AN EXTERNAL IRB: (REQUIRED) Does this application include a request to rely external IRB (a central IRB (other than the NCI CIRB) or an external IRB (other UC campus, commercial, or institutional): ○ Yes No 7.0 Research Plan and Procedures 7.1 HYPOTHESIS: Describe the hypothesis or what the study hopes to prove: 	on an

Hypothesis 2: Participants randomized to the 8-week digital meditation intervention will report greater increases in subjective mindfulness, as measured by the Mindful Awareness and Attention Scale, compared to those in the waitlist control condition. The increase in mindfulness will statistically mediate improvements in global stress perception and job strain.

Hypothesis 3: Treatment adherence to the 8-week digital meditation intervention will moderate observed treatment effects, such that improvements in global stress perception and job strain will be stronger among participants who completed more meditations.

Sub-study:

Hypothesis 1. Compared to the Waitlist control condition, participants randomized Digital Meditation, Healthy Eating, or Digital Mediation+Healthy Eating will show greater decreases in blood pressure, improvements in metabolic outcomes, and improvements in measures of psychological stress. Effects will be strongest in the Digital Meditation+Healthy Eating condition.

7.2 AIMS: List the specific aims:

Aim 1: To test the effects of a digital meditation intervention, compared to a waitlist control condition, on global perceptions of stress and job strain in a sample of UCSF employees.

Aim 2: To identify whether increases in mindfulness serves as a pathway through which digital meditation affects reports of stress and test whether treatment adherence moderates treatment-related stress effects.

Sub-study

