Re-engagement protocol: As with any digital intervention study, attrition is common. In an effort to minimize attrition in this study, we have developed a re-engagement protocol. We will send an engagement text message to each participant starting about one week into their participation and for each subsequent week, for 7 weeks. The text message content for the intervention group will consist of gentle reminders to continue to meditate, along with tips to stay active and engaged in the study. For the waitlist control group, these weekly messages will consist of encouragements and brief reminders of participation requirements (see attached doc for specific text). If a participant does not engage after about 2 weeks, then he/she will receive a phone call from our research staff. For those participants who do not answer the phone, the study staff will leave a voicemail and a subsequent text message asking to call them back, and follow up again the next day with another text message. They only hear back from the staff in 2 weeks if they continue to refrain from the meditation app.

Sub-study: Participants will follow the same re-engagement protocol listed above, with minor modifications for the healthy eating groups.

Those in the healthy eating groups will participate in 3 separate booster phone calls (5-10 minutes) to check-in regarding progress and barriers towards healthy eating goals, and feasibility/acceptability of the brief eating intervention. Participants will receive automated text message pings approximately 3 times per week. The pings will provide reminders about mindful eating (including a link to audio sessions on cravings and mindful eating). The pings will occur during identified times of "high vulnerability" from the initial counseling session.

7.10 STANDARD CLINICAL PRACTICE: To what extent, if any, do the planned research procedures differ from the care that people would otherwise receive at this institution or the study site if not being done locally:

The standard care that participants receive will not change.

7.11 INSTRUMENTS: List all questionnaires, surveys, interview, or focus group guides that will be used for this study:

If the instruments are not complete or not available because they will be developed as part of this study, describe the basic content or include an outline and submit the final versions to the IRB with a modification for approval prior to use.

Eligibility Screening.

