Palatable Eating Motives: Coping Subscale (PEMS) (Burgess, Turan, Lokken, Morse, & Boggiano, 2014). The PEMS Coping subscale is comprised of 4 Likert-like five-choice frequency response items that probe various motives for "eating tasty food and drinks." The instructions include a list of examples of these kinds of foods and sugary drinks. The list of tasty foods was adopted from the Yale Food Addiction Scale (Gearhardt, Corbin, & Brownell, 2009) with slight modifications. The Coping motives subscale measures intentionally using palatable food to cope with negative feelings (e.g., to forget about or help with worry, depression, nervousness, a bad mood, or problems). Item response choices range from almost never /never to almost always/always. The trait form for this subscale has been validated using ecological momentary assessment, and both versions are related equally to BMI and changes in emotional eating correlate with changes in BMI over time (Boggiano, Wenger, Turan, Tatum, Morgan, et al., 2015; Boggiano, Wenger, Turan, Tatum, Sylvester, et al., 2015).

Attach any unpublished instruments in the 'Other Study Documents' section of the Initial Review Submission Packet form after completing the study application. Published instruments should NOT be attached.

7.12 * BIOSPECIMEN COLLECTION: Are you drawing any blood or collecting other biosamples (e.g. tissue, buccal swabs, urine, saliva, hair, etc.) for analysis under this protocol and/or storage for future research: (REQUIRED)

O Yes O No

7.13 STATISTICAL METHODS: Briefly summarize the methods and types of analyses that will be performed:

We will employ chi-square and *t*-tests to examine group difference in baseline in demographics and measures obtained by our baseline questionnaire. Intervention effects on each outcome were tested using linear mixed models with Time (t1 and t2) was included as a within-person factor and intervention group as a between-person factor. We will analyze the data using an intent-to-treat framework, and carry forward latest data point in our final analysis. Alpha's were set at .05 for each outcome. We used eta-squared as our effect size index.

To investigate dose response effects, we will examine whether number of medication sessions moderates the interventon effects among those in the digital meditation group. In this regard, we will test a 2-way interaction (number of weekly meditation*time). All analyses will be conducted in SPSS Version 24 and STATA 13.1.

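### Section 7.13 labels a sessions-by-time slope within the app arm as dose response and as moderation of the intervention effect; it can support only an observational association

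*Combined protocol and SAP*

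**What the plan says.** Hypothesis 3 (section 7.1) has two parts. The main clause is causal in form: "Treatment adherence to the 8-week digital meditation intervention will moderate observed treatment effects". The second clause says what would be seen: "such that improvements in global stress perception and job strain will be stronger among participants who completed more meditations". Aim 2 (section 7.2) repeats the causal form; the study is to "test whether treatment adherence moderates treatment-related stress effects".

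Section 7.13 tests intervention effects with a mixed model that has "intervention group as a between-person factor". Its next paragraph turns to dose response: "we will examine whether number of medication sessions moderates the interventon effects among those in the digital meditation group" (meditation sessions are evidently meant). The test is described as follows: "we will test a 2-way interaction (number of weekly meditation*time". No group term appears. For missing data the section says the investigators will "carry forward latest data point in our final analysis".

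Under section 7.9 everyone in the app arm gets the same instruction of one short session a day, and use is tracked through the app. The re-engagement protocol adds: "If a participant does not engage after about 2 weeks, then he/she will receive a phone call from our research staff".

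The SAP appended after section 16.0 contains only a four-group ANCOVA at week 8. It has no adherence analysis, and nothing in either part labels this analysis exploratory or observational.

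**The concern.** By the section's own definition, an intervention effect is a difference between randomised groups over time. The adherence test drops the group, so sessions can only be related to pre-post change in one arm. That change includes whatever would have happened without the app. Session count is also an outcome of randomisation, not an assigned dose. Motivation, workload or prognosis may drive both use and improvement, and staff contact itself depends on use.

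At stake is the status of one named hypothesis and half of Aim 2. As worded, a significant slope among self-selected users could be reported as dose response and as confirmed moderation.

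**Working it through.** The plan gives no effect size, SD, dropout rate or power for this test, so there is no figure to reproduce.

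**Inputs from the documents.** App arm of 1,000 (section 9.1), or 500 if the 1,000 in section 4.1 is the total; alpha 0.05 per outcome (section 7.13), taken as two-sided; two time points (section 7.13); attrition expected but no rate given (sections 7.9 and 9.3); entry at a PSS of 15 or higher (inclusion criteria). Everything else below is an assumption.

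**Step 1: what the slope estimates.** With two time points, the sessions-by-time coefficient is the regression of change on sessions, b = Cov(S, change) / Var(S). Split each person's change into the part that would occur without the app, C, and the app's effect, E:

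b = Cov(S, C)/Var(S) + Cov(S, E)/Var(S).

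Moderation concerns only the second term. The first can be separated only with information from untreated people, and the model has none. Even the second term says who benefits more, not what extra sessions would do, because S is self-chosen.

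**Step 2: size of the self-selection route.** Set E = 0 and let r be the correlation of sessions with untreated change. With complete data the rejection rate is approximately Φ(√(n−3) × atanh(r) − 1.96). For n = 1,000 and r = 0.10: 31.58 × 0.1003 = 3.17; 3.17 − 1.96 = 1.21; Φ = 89%.

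| r | n = 1,000 | n = 500 |
|---|---|---|
| 0 | 5% | 5% |
| 0.05 | 35% | 20% |
| 0.10 | 89% | 61% |
| 0.15 | 99.8% | 92% |

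With an SD of change of 5 and an SD of weekly sessions of 1.7, r = 0.05 is a slope of 0.05 × 5/1.7 = 0.15 points per weekly session, and r = 0.10 is 0.29. Very weak selection is enough.

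**Step 3: the carry-forward route, if the rule applies.** Set r = 0 and E = 0. Assume weekly sessions of 3 ± 1.8 limited to 0-7; an SD of change of 5 at weeks 4 and 8, correlated 0.6; 30% dropout, half of it before week 4 (baseline carried) and half after (week 4 carried); and a 2-point untreated fall by week 8. Dropouts miss part of the fall. If half the fall comes by week 4, the mean shortfall per dropout is 0.5 × 2 + 0.5 × 1 = 1.5 points. If all of it comes by week 4, the shortfall is 0.5 × 2 = 1.0. When low users drop out more, this shortfall falls mainly on them and appears as a slope. Simulated rejection rates, good to about a percentage point:

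| Dropout odds per SD more sessions | Share of fall by week 4 | n = 1,000 | n = 500 |
|---|---|---|---|
| ×0.37 | half | 44% | 23% |
| ×0.37 | all | 23% | 13% |
| ×0.61 | half | 17% | 11% |
| ×0.61 | all | 9-10% | 7% |

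With no untreated fall, or no link between sessions and dropout, the rate is about 5%.

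**Step 4: does using observed data help?** A likelihood analysis that includes week 4 gives 4-6% with a mean slope of 0.00, even when dropout depends on week-4 change (odds ×1.5 per SD). Two-point complete cases under dropout that depends on week-4 change give roughly 9-15% at n = 1,000, so the week 4 values matter. Neither analysis touches the self-selection route in step 2.

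**The case against.** The fair defence is that the test answers the second clause of Hypothesis 3 exactly as written: did people who completed more sessions improve more? That stands, and the slope is worth reporting. What does not follow is the main clause, Aim 2, or the dose-response label.

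Several stronger readings are tempting, and the documents do not support them.

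- *The test certainly uses carried-forward values.* The rule stands in the intent-to-treat sentence and is not repeated in the dose paragraph. Applying it here is natural but not explicit. The point stands without it.
- *Carry-forward will create a false slope.* It does so only if low users drop out more and stress falls untreated, and the documents quantify neither. The PSS threshold makes some fall plausible, but PSS is measured at screening and again at baseline, so part of it may precede the first time point. Job strain has no threshold.
- *Phoning non-engagers inflates the slope.* If contact helps, it would flatten the slope. The direction is unknown.
- *Adding the waitlist would cure it.* App sessions are undefined in that arm.

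It is also true that the figures in step 2 are simply power to detect an assumed correlation and would apply to any observational analysis. That is the reason for the label. Finally, section 7.13 is meant as a brief summary, and section 7.5 reports the earlier adherence result as an association. The same wording here would remove the concern.

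**Conclusion.** The point holds for what the analysis can support. A within-arm slope on self-chosen session counts describes an association between use and improvement. It does not test moderation of the treatment effect or a causal dose response, and nothing in the SAP repairs this. That conclusion follows from the text and needs no numerical assumption.

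The numbers show only how easily a significant slope arises with no app effect. A correlation of 0.05 to 0.15 gives 35% to 99.8% at 1,000 in the app arm, and 20% to 92% at 500. The conditional carry-forward route adds about 9-44% or 7-23% under 30% dropout and a 2-point fall. The upper ends need strongly session-related dropout and a fall that is only half complete by week 4.

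A reader might infer that the trial's main result is in doubt. It is not: the randomised comparison does not use this test. The change should be made because a named hypothesis could otherwise be declared confirmed on observational evidence.

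**What to change.** In section 7.13, replace the dose-response text with:

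> Among participants assigned to the app we will report the sessions*time slope with a 95% CI from a likelihood-based mixed model on all observed baseline, week 4 and week 8 values, without carried-forward values. Session count is not randomised, so this is an exploratory observational association and will not be reported as dose response or as moderation of the intervention effect.

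Reword Hypothesis 3 (section 7.1) and the adherence part of Aim 2 (section 7.2) to match: an association, within the app arm, between sessions completed and improvement in perceived stress and job strain.

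The cost is wording in three sections and a slightly larger model. No new data are needed, because section 7.11 already collects both outcomes at week 4. The real price is that the trial then has no confirmatory test of adherence as a moderator. The current design does not provide one either.

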8.0 Drugs and Devices

	approved or unapproved: (REQUIRED)	
0	Yes • No	
83	* MEDICAL DEVICES: Are you STUDYING any medical devices in vitro diagnostics or assays the	at are

8.3 * MEDICAL DEVICES: Are you STUDYING any medical devices, in vitro diagnostics, or assays that are either approved or unapproved:(REQUIRED)

○ Yes No

9.0 Sample Size and Eligibility Criteria	
9.1 ENROLLMENT TARGET: How many people will you enroll:	
10000	
If there are multiple participant groups, indicate how many people will be in each group:	
We will screen a high number of potential participants to carry out this study. In this regard, we will screen as many as 10000 individuals and thus as many as 10000 individuals will complete a consent form to be screened. Of those who complete the screening, we anticipate that we will consent into the study 2000 participants. We will randomize 1000 participants to our digital mediation condition (Headspace) and 1000 to the waitlist control condition.	
9.3 SAMPLE SIZE JUSTIFICATION: Explain how and why the number of people was chosen. For mul studies, this is referring to the number that will be enrolled across all sites:	lti-site
We are interested in testing a digital intervention with limited contact by study investigators (i.e., no in person contact). As such, participant attrition is to be expected. Our prior study (Bostock et al., under revision) detected effects in a sample of < 250 participants. We expect that our sample size will be well powered to detect improvements in our self-report measures in response to our treatment intervention.	
9.4 * PARTICIPANT AGE RANGE: Eligible age ranges: (REQUIRED)	
 □ 0-6 years □ 7-12 years □ 13-17 years ☑ 18-64 years ☑ 65+ 	
9.5 * STUDY POPULATIONS: Data will be collected from or about the following types of people (che that apply): (REQUIRED)	eck all
☐ Inpatients ☐ Outpatients	
Family members or caregivers Providers	
People who have a condition but who are not being seen as patients Healthy volunteers	
☐ Students ☑ Staff of UCSF or affiliated institutions	
☐ None of the above	
9.6 * SPECIAL SUBJECT GROUPS: Check the populations that may be enrolled: (REQUIRED)	
 □ Children / Minors □ Adult subjects unable to consent for themselves □ Adult subjects unable to consent for themselves (emergency setting) 	
Subjects with diminished capacity to consent Subjects unable to read, speak or understand English	
☐ Pregnant women ☐ Fetuses	
☐ Neonates ☐ Prisoners	
Economically or educationally disadvantaged persons	

V	None of the above	
	INCLUSION CRITERIA: Briefly describe the population(s) that will be involved in this study. Incampone that data will be collected from or about (e.g. patients, healthy controls, caregivers, proadministrators, students, parents, family members, etc.):	
Λ σιι	bject will be eligible for inclusion in this study only if all of the following criteria apply:	
	Have access to a smartphone or computer every day	
	Fluent in English and has at least a third grade reading level	
	Is a UCSF employee	
	Perceived Stress Scale total of score of 15 or higher	
	 Consent: demonstrates understanding of the study and willingness to participate as evidenced by voluntary informed consent and has received a signed and dated copy of the informed consent form 	
	• Is at least 18 years of age	
	• Expresses willingness to be randomly assigned into with the waitlist group or the intervention group	
Subs	study participants must report a BMI of 25 or above	
	EXCLUSION CRITERIA: List any exclusion criteria (e.g. reasons why someone would not be incluthe study):	uded in
A su	bject will not be eligible for inclusion in this study if any of the following criteria apply:	
	 Experienced meditator and/or report current (three times per week or more- for 10 minutes at a time) sitting meditiation practice 	
	* RESEARCH CONDUCTED ON PATIENT CARE WARDS: Do any study activities take place on any care units including inpatient wards, peri- or post-operative care units, operating rooms, or in temergency Department at UCSF Health medical facilities: (REQUIRED)	
0	Yes © No	
9.11	* EMERGENCY DEPARTMENT: Does your protocol or study involve any of the following patient activities in the emergency department (e.g. subject identification, recruitment, consent, bloo draws, specimen retrieval, involvement of ED staff (nursing, tech, and/or physician), or any or based procedures): (REQUIRED)	d
0	Yes • No	
10.0	Recruitment and Consent	
10.1	* COMPETITIVE ENROLLMENT: Is this a competitive enrollment clinical trial? By competitive enrollment, we mean that sites who do not enroll participants early may not get to participate (REQUIRED)	at all:
0	Yes © No	
10.2	* SUBJECT IDENTIFICATION METHODS: What kinds of methods will be used to identify potent	ial

Review of patients' conditions, history, test results, etc. (includes patients seen in clinic, scheduled for surgery, a procedure, imaging, or tests, or seen in the Emergency Department as well as searching through medical record data for possible cohort identification) Already approved recruitment registry Re-contact of participants from the investigators' previous studies Referrals from colleagues (attach the 'Dear Colleague' letter or other recruitment materials you will provide to colleagues) Referrals from the community / word of mouth Advertisements (flyers, brochures, radio or t.v. ads, posting on clinical research sites or social media, presentation of the study at community events/media, etc.) Online recruiting tool (describe below) CTSI Recruitment Services unit Posting on UCSF Clinical Trials, ClinicalTrials.gov or other publicly available clinical trial website Other method (describe below) Attach your recruitment materials (e.g., flyers, ads, recruitment letter templates, email text, etc.) in the Other Study Documents section of the Initial Review Submission Packet Form. * Provide details about the subject identification methods: (REQUIRED) UCSF employees will be recruited through flyers, staff events, email, etc. * Did all the participants of previous studies provide permission to be contacted for future studies: (REQUIRED)	
Yes O No	
10.4 DETERMINATION OF ELIGIBILITY: How, when, and by whom will eligibility for recruitment be determined:	
Any UCSF employees will be eligible for recruitment. They will be targeted at UCSF campuses and utilizing university services such as flyers, advertisements, digital media, emails through listservs. We expect to	
reach as many as 10,000 individuals. Those interested in participation will inquire on the website for more details, and their eligibility for the study will be determined by the screening questionnaire. If they are eligible, they will have the option to consent and will be invited into the study via an automated email.	
Those interested in participation will inquire on the website for more details, and their eligibility for the study will be determined by the screening questionnaire. If they are eligible, they will have the option to	
Those interested in participation will inquire on the website for more details, and their eligibility for the study will be determined by the screening questionnaire. If they are eligible, they will have the option to consent and will be invited into the study via an automated email.	
Those interested in participation will inquire on the website for more details, and their eligibility for the study will be determined by the screening questionnaire. If they are eligible, they will have the option to consent and will be invited into the study via an automated email. 10.5 * INITIATION OF CONTACT: Who initiates contact (check all that apply): (REQUIRED) Investigators/study team UCSF recruitment unit (e.g. CTSI Consultation Services) Potential participant	

Attach the recruitment letter or email template in the Other Study Documents section of the Initial Review Submission Packet Form.

Provide the URL for any website in Recruitment Plan section, or attach a mock-up of the website or the app screens in the Other Study Documents section of the Initial Review Submission Packet Form.

- 10.7 RECRUITMENT PLAN: Based on the checkboxes you chose above, please provide a narrative describing your recruitment plan. We want to know:
 - Who is conducting the search for potential participants, and how?
 - How are potential subjects being approached for recruitment? By whom, and when?

If there will be more than one participant group (e.g. patients, healthy controls, caregivers, family members, providers, etc.), provide details about the recruitment plans for each group.

(Recommended length - 100-250 words)

The research staff, including a clinical research coordinator and research assistants, will recruit participants using several strategies, including:

- Flyers at each of the UCSF campuses, including in cafeterias and other areas of high traffic areas, such as UCSF Shuttles
- UCSF wide emails via announcements and staff listservs (email blasts)
- Digital advertisements posted on screens around campus and on social media
- Announcements about the study in lectures or other on-campus events
- * CONSENT METHODS: How will permission to participate (i.e., informed consent) be obtained from each potential participant. If there will be multiple groups and different plans for consenting each, check all that apply. See the orange Help bubble to the right for more detailed guidance. Participants will (check all that apply): (REQUIRED)

✓ Sign a consent form at the end of the consent discussion (signed consent)
Click through a link in a survey or email after reading about the study and then complete the study online (electronic consent)
☐ Be told about the study and be given a handout/information sheet and be asked if they agree to participate (verbal consent)
Complete the study activities and turn in materials, as in the case of a completed survey that is placed in a drop box or mailed to the study team (implied consent)
☐ Not be able to provide consent and will have a family member consent for them, as in the case of a critically ill or unconscious patient (surrogate consent)
☐ Not be able to provide consent (emergency waiver of consent - allowed for minimal risk research or greater than minimal risk research with an approved community consultation plan)
■ Not know about the study, as in the case of chart reviews or observations of public behavior (waiver of consent)
☐ Other method (describe below)
Attach your consent form, information sheet, or electronic consent text in the Informed Consent Documents section of the Initial Review Submission Packet Form.

- * CONSENT PROCESS: Describe the process for obtaining informed consent, including details such as who will have the consent discussion and when participants will be asked to sign the consent form in relation to finding out about the study: (REQUIRED) We encourage researchers to review our guidance on obtaining and documenting informed consent.
 - If there are multiple groups being consented differently, provide details about the consent process for each group.

•	If you are relying on	verbal or implied	consent, prov	ide details abou	it how that will happen

• For studies using online recruitment and consent or consent via mail, provide details here.

Potential participants will go to the website of our study and on the homepage, they can choose to "join the study." After completing the eligibility screening questionnaire, eligible participants will be routed to the online informed consent page, with the bill of rights and the complete IRB approved informed consent document. They will be provided detailed information about the study and will be instructed to read through and check the box confirming that they "have read, understood and agreed to the consent process." They will have the option to print or save the document as a pdf. They will also be provided with a study email address as a contact if they have specific questions. They will be informed of their voluntary participation and that none of the information collected will have any impact on their employment at UCSF.

Sub-study: Potential participants will read and sign a printed version of the informed consent at the end of the consent discussion at the first in-person assessment. The study staff will provide a signed copy to the participant if requested, and save a copy in a secure, locked location in the lab.

* It is important that the people obtaining consent are qualified to do so. Briefly describe the training and experience these individuals have in obtaining informed consent: (REQUIRED)

All Research Assistants will complete thorough training on consent process, including reviews of IRB protocol, undergo HIPAA certification, and are required to complete CITI training.

10.10	* CONSENT COMPREHENSION: Indicate how the study team will assess and enhance the subjunderstanding of study procedures, risks, and benefits prior to signing the consent form (che that apply): (REQUIRED) Tip: Review the Consent Comprehension - Learning Notes in the Hobubble at the right for specific questions that can be asked to assess comprehension, considerusing the UCSF Decision-Making Capacity Assesment Tool, and review our guidance on obtain written or verbal informed consent for more detail on how to conduct the assessment.	ck all elp r
the	e study team will engage the potential participant in a dialogue, using open-ended questions about a nature of the study or the experimental treatment, the risks and benefits of participating, and the luntary nature of participation	
- D. J	tankial mankisinanta will be asleed an abawwa a social of avertions to assess their wadawstanding of the	

✓ Potential participants will be asked or shown a series of questions to assess their understanding of the study purpose, procedures, risks and benefits, as well as the voluntary nature of participation (especially appropriate when the consent process happens online or through a mobile health app)

Other method (describe below):

Provide details of the other approaches that will be used, if using another method to assess comprehension:

10.11 * DECEPTION: Does this study rely on some deception or misinformation about what the researchers are observing to get valid data? (REQUIRED)

O Yes 💿 No

10.13 * WAIVER OF DOCUMENTATION OF SIGNED CONSENT: Select the regulatory category under which the IRB may waive the requirement to obtain *signed* consent for this study:

- The only record linking the subject and the research would be the consent document and the principal risk would be potential harm resulting from a breach of confidentiality. Each subject will be asked whether they want documentation linking them with the research. 46.117(c) (1)
- The research presents no more than minimal risk of harm to subjects and involves no procedures for which written consent is normally required outside of the research context. 46.117(c) (2)

10.14 TIME: What is the estimated time commitment for participants (per visit and in total):

The proposed study is designed to be carried out digitally with limited contact with study staff. All participants will be asked to complete our questionnaire batteries at baseline, week 4, week 8 and + 4 months, and participants randomized to the digital meditation condition will be asked to complete + 1 year follow up questionnaire battery. The questionnaires included at the baseline and week 8 time points require 20 minutes to complete while the questionaires completed at the other time points are much shorter, requiring between 5 to 10 minutes each time. Additionally, participants randomized to the digital meditation condition will be asked to use the Headspace app each day (10 minutes daily) over the 8 week study.	
Sub-study: All participants in the sub-sample will be asked to complete questionnaire batteries at baseline, week 4, week 8 and + 4 months, and participants randomized to the digital meditation condition will be asked to complete + 1 year follow up questionnaire battery. The questionnaires included at the baseline and week 8 time points require about 30-35 minutes to complete while the questionnaires completed at the other time points are much shorter, requiring between 5 to 10 minutes each time.	
In person assessments: The first in-person assessment will last no longer than 60 minutes, and the final assessment is estimated to require 30 minutes, not counting transportation to the meetings.	
Daily diary: There will be fourteen total surveys, each lasting about 3-5 minutes.	
Headspace meditations: The digital meditation condition will be asked to use the Headspace app each day (10 minutes daily) over the 8 week study.	
Healthy eating program: Either one of the conditions including the healthy eating program will be involved in additional activities. First, a phone call to schedule the counseling session is expected to last about 5-10 minutes, while the counseling visit itself is estimated to last 30 minutes. Next, the 3 phone calls received throughout the duration of the intervention will last about 5-10 minutes each. The audio modules require about 5 minutes each, but are completely optional.	
IMPORTANT TIP: Ensure this information is consistent with the information provided in the consent form.	
10.15 ALTERNATIVES: Is there a standard of care (SOC) or usual care that would be offered to prospective participants at UCSF (or the study site) if they did not participate in this resea study:	rch
O Yes ⊙ No	
10.16 OFF-STUDY TREATMENT: Is the study drug or treatment available off-study:	
• Yes • No • No • Not applicable	
10.17 OTHER ALTERNATIVES: Describe other alternatives to study participation, if any, that are avaito prospective subjects:	ailable

